7.6.7 Physical Examination Findings

All physical examination abnormal findings will be listed per subject.

7.6.8 Daily Urinary Output

Urinary output is collected from start of infusion to 3 hours after end of infusion in each treatment period. Daily urinary output will be summarized descriptively for all safety population by treatment for each time point.

7.6.9 *Oxygen Saturation*

Peripheral Oxygen Saturation is collected prior to the infusion and after end of infusion in each treatment period. Oxygen Saturation will be summarized descriptively for all safety population by treatment for each time point as well as change from baseline.

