2 SCHEDULE OF ACTIVITIES

Table 2-1: Time & Event Schedule CV013020, Screening Period

Procedure	Screening Visit	Notes
Eligibility Assessments		
Informed Consent	x	A participant is considered enrolled only when a protocol specific informed consent is signed.
Inclusion/Exclusion Criteria	x	
Medical History	x	
Concomitant medications	x	
Echocardiography eligibility assessment	x	As described in the echocardiographic core lab manual, evaluation of image quality and assessment of ejection fraction
Safety Assessments		
Physical Examination	x	If the screening physical examination is performed within 3 days prior to first dosing then a single exam may count as both the screening and pre-dose evaluation. Includes height and weight.
Vital Signs	x	Includes body temperature, respiratory rate, and seated blood pressure and heart rate. Blood pressure and heart rate should be measured after the participant has been resting quietly for at least 5 minutes.
Adverse Events Assessment	x	SAEs must be collected from the date of the participant's Informed consent.
Local Laboratory Tests	x	Hematology, Serum chemistry, NT-proBNP or BNP (details in the protocol section 9.4.4)
Pregnancy Test (WOCBP only)	x	

Table 2-2: Time & Event Schedule CV013020, Treatment and Follow-up Study Periods

Procedure	Treatment Period					Notes
	Period 1 Day 1	Washout 5-28 Days	Period 2 Day 1	Washout 5-28 Days	Period 3 Day 1	
Safety Assessments						Washout between periods should be at least 5 days and no more than 4 weeks.
Weight	x		x		x	Weight pre-and end of the infusion in each treatment period.
Targeted physical examination	x		x		x	Based on subject's report since the screening visit. Includes temperature, signs and symptoms of congestion.
Vital Signs (Blood pressure and heart rate)	x		x		x	Prior to infusion. 30 minutes at first hour, then every 1 hour until discontinuation of infusion, then at 1 hour, 2 hour and 3.5 hour after end of infusion in each treatment period.
Peripheral Oxygen Saturation	x		x		x	Prior and end of the infusion in each treatment period, measured with a pulse oximeter device.
12 lead ECG	x		x		x	Prior to the infusion and after end of infusion in each treatment period.
Urinary output	x		x		x	From start of infusion to 3 hours after end of infusion in each treatment period.
Telemetry	x		x		x	From start of infusion to 3 hours after end of infusion in each treatment period.

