The administration of the study drugs will be done through an infusion pump connected to a single peripheral IV line. After priming the infusion set tubing and connecting the lines to the intravenous catheter, the pump should be set to deliver the rates of infusion indicated on the infusion bag label according to the up-titration schedule (See [Section 5.1](#)).

The pump infusion volume display should be re-set to 0 after priming the infusion line and just prior to the start of the infusion, and the total volume infused at the conclusion of the infusion after 5-hours, or at the time of any early discontinuation, should be recorded in the clinic source documents.

[figure not shown]
At any time during the administration of study drug, the study drug infusion must be discontinued if an adverse event or any other safety issue suggests it is not in the patient's best interest to continue to receive study drug.

The investigator has the option to adjust the study drug dosage level downward by 50%, interrupt or discontinue the study drug infusion in patients that develop hypotension, or if the patient experiences symptomatic hypotension that is not easily tolerated, as follows (and shown in Figure 7.4-1)

- **Study drug reduction:** Study drug is decreased by 50% if SBP decreases to levels <90 mmHg but ≥ 80 mmHg. The dose cannot be subsequently increased.
- **Study drug interruption:** Study drug is interrupted for 1 hour if SBP decreases to <80 mmHg or symptoms of low blood pressure occur within the first 4 hours of infusion. If the SBP is ≥ 105 mmHg after one hour interruption, the study drug could be resumed at 50 % of the dose to complete 5-hours of effective study drug infusion.
- **Study drug discontinuation:** Study drug will be permanently discontinued if SBP remains < 105 mmHg after 1 hour interruption or if SBP decreases to levels <80 mmHg or symptoms of low blood pressure occur after 4 hours of infusion.

End of infusion procedures should be done as soon as possible after interruption or discontinuation of the study drug. If an infusion in a given period is discontinued, patients remain eligible to complete subsequent periods.

Figure 7.4-1: BP Management Algorithm

Any decision to lower the dosage level of study drug or discontinue study drug should be based on the investigator's assessment of the patient's overall clinical stability, in the context of appropriate ongoing monitoring of the patient's condition.

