7.7 Concomitant Therapy

7.7.1 Prohibited and/or Restricted Treatments

- Initiation of PDE5 inhibitors is prohibited during study drug infusion and 24 hours after the end of the study drug.

- Administration of IV vasoactive drugs (such as dopamine, dobutamine, enoximone, nitroprusside, levosimendan or milrinone) is not permitted during study drug infusion
- Chronic oral heart failure medications (diuretics, ACE inhibitors, ARBs, MRA, beta-blockers, calcium antagonists) will be withheld in the morning of the treatment day and will be administered after the end of the study drug infusion
- Initiation of chronic oral, transdermal or sublingual nitrates is prohibited during the treatment period.

7.7.2 *Other Restrictions and Precautions*

Not applicable

7.7.2.1 *Imaging Restriction and Precautions*

Not applicable.

7.8 *Treatment After the End of the Study*

At the end of the study, BMS will not continue to provide BMS supplied study treatment to participants/investigators unless BMS chooses to extend the study. The investigator should ensure that the participant receives appropriate standard of care to treat the condition under study.

8 *DISCONTINUATION CRITERIA*

8.1 *Discontinuation from Study Treatment*

Participants MUST discontinue investigational product (and non-investigational product at the discretion of the investigator) for any of the following reasons:

- Participant's request to stop study treatment. Participants who request to discontinue study treatment will remain in the study and must continue to be followed for protocol specified follow-up procedures. The only exception to this is when a participant specifically withdraws consent for any further contact with him/her or persons previously authorized by the participant to provide this information
- Any clinical adverse event (AE), laboratory abnormality or inter-current illness which, in the opinion of the investigator, indicates that continued participation in the study is not in the best interest of the participant
- Termination of the study by Bristol-Myers Squibb (BMS)
- Loss of ability to freely provide consent through imprisonment or involuntarily incarceration for treatment of either a psychiatric or physical (e.g., infectious disease) illness
- If study medication has been interrupted for low blood pressure, resumed, and an episode of hypotension (or symptoms of hypotension) reoccurs

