2 STUDY DESCRIPTION

2.1 Study Design

This is a multi-center, randomized, cross-over, placebo and active-controlled, double-blind, study of continuous 5-hour intravenous (IV) infusions of BMS-986231 in patients with heart failure and reduced ejection fraction (HFrEF). The trial is designed to evaluate the effects of BMS-986231 on systolic and diastolic parameters measured by echocardiography.

A cross-over design will be implemented in this trial; every subject will be exposed to each of the 3 interventions (BMS-986231, Nitroglycerin (NTG) and placebo) in 3 treatment periods. Each treatment period will include one intervention occurring via 5-hour infusion, followed by a washout period of at least 7 days, but no more than 4 weeks.

42 study participants will be randomized to receive BMS-986231, NTG, and placebo, in one of the 6 possible sequences.

NTG, BMS-986231 and placebo will be administered as a 5-hours infusion according to an uptitration schedule, which is achieved by an increase in the infusion flow rate. All three interventions (NTG, BMS-986231 and placebo) will have the same flow rate: 5 mL/H for 10 min, followed by 10 mL/H for 10 minutes then 20 mL/H for the rest of the infusion.

[figure not shown]
The corresponding doses of the active study medications will be:

- NTG: 20 $\mu\text{g}/\text{min}$ for 10 min, followed by 40 $\mu\text{g}/\text{min}$ for 10 min, followed by 80 $\mu\text{g}/\text{min}$ for the rest of the 5-hour infusion;
- BMS-986231: 3 $\mu\text{g}/\text{kg}/\text{min}$ for 10 min, followed by 6 $\mu\text{g}/\text{kg}/\text{min}$ for 10 min, followed by 12 $\mu\text{g}/\text{kg}/\text{min}$ for the rest of the 5-hour infusion.

In case of a decrease in systolic blood pressure, an algorithm will be used to down-titrate /interrupt or discontinue the study drug infusion (see protocol [Section 7.4](#)).

The study design schematic is presented in Figure [2.1-1](#).

Figure 2.1-1: Study Design

*Wash-out period will be at least 7 days and no more than 4 weeks

Screening

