7.4 Extent of Exposure

At any time during the administration of study drug, the study drug infusion must be discontinued if an adverse event or any other safety issue suggests it is not in the patient's best interest to continue to receive study drug.

The investigator has the option to adjust the study drug dosage level downward by 50%, interrupt, or discontinue the study drug infusion in patients that develop hypotension, or if the patient experiences symptomatic hypotension that is not easily tolerated, as follows

- Study drug reduction: Study drug is decreased by 50% if SBP decreases to levels <90 mmHg but ≥ 80 mmHg. The dose cannot be subsequently increased.
- Study drug interruption: Study drug is interrupted for 1 hour if SBP decreases to <80 mmHg or symptoms of low blood pressure occur within the first 4 hours of infusion. If the SBP is ≥ 105 mmHg after one hour interruption, the study drug could be resumed at 50 % of the dose to complete 5-hours of effective study drug infusion.
- Study drug discontinuation: Study drug will be permanently discontinued if SBP remains < 105 mmHg after 1 hour interruption or if SBP decreases to levels <80 mmHg or symptoms of low blood pressure occur after 4 hours of infusion.

End of infusion procedures should be done as soon as possible after interruption or discontinuation of the study drug. If an infusion in a given period is discontinued, patients remain eligible to complete subsequent periods.

Study drug administration and randomization schedule will be documented as per subject listings. The number and percentage of subjects with dose interruptions, dose reductions, and

dosing discontinuations will also be summarized and listed by treatment group for the safety population.

Any non-study medications taken by subjects, any conducted non-study medical treatment procedures, and any utilized non-study diagnostic procedures will also be listed.

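### Urinary output is summarised as a daily figure with no scaling, although the collection window can run from just over 3 h to about 9 h depending on how the infusion went

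*SAP*

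**What the plan says.** SAP 7.6.8 defines the collection: "Urinary output is collected from start of infusion to 3 hours after end of infusion in each treatment period". The protocol's Schedule of Activities (Table 2-2) gives the same window: "From start of infusion to 3 hours after end of infusion in each treatment period". The SAP then plans the summary: "Daily urinary output will be summarized descriptively for all safety population by treatment for each time point". It mentions no division by hours collected and no handling of short or long collections. It does not define *daily* or the time points.

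The end of infusion, which closes the window, is not fixed:

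- The plan is a 5 h infusion (SAP 2.1): "NTG, BMS-986231 and placebo will be administered as a 5-hours infusion according to an uptitration schedule".
- It may be paused (SAP 7.4): "Study drug is interrupted for 1 hour if SBP decreases to <80 mmHg or symptoms of low blood pressure occur within the first 4 hours". Once blood pressure has recovered, "the study drug could be resumed at 50 % of the dose to complete 5-hours of effective study drug infusion" (Protocol 7.4, repeated in SAP 7.4).
- It may end early. SAP 7.4 says: "At any time during the administration of study drug, the study drug infusion must be discontinued if an adverse event" or another safety issue makes continuing contrary to the patient's interest. No minimum infusion time is set.
- A second hypotensive episode ends it. Protocol 8.1 lists this among the mandatory reasons to stop: "If study medication has been interrupted for low blood pressure, resumed, and an episode of hypotension (or symptoms of hypotension) reoccurs".

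Patients who stop early stay in the table, because the Safety Population (SAP 6.3) requires only one dose. Interrupted infusions that are not permanently stopped count as completed (SAP 7.3, Subject Disposition). Patients are normally discharged about 3.5 h after dosing (SAP 2.1), so no 24 h collection is planned.

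**The concern.** A volume collected over a window of varying length reflects both how fast urine was produced and how long it was collected. Here the length is set by the blood-pressure algorithm and by adverse events, so it depends on how well the infusion was tolerated.

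Protocol 9.3 describes BMS-986231 as vasodilating, with hypotension arising in part by mechanisms similar to those of nitroglycerin. Placebo is 5% dextrose. It is therefore plausible that the two active treatments will have more stops and interruptions than placebo. If so, early stops would lower the recorded volume on the active treatments and interruptions would raise it, with no renal effect in either case. A reader of the table could not separate the two.

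The label adds to the problem. A daily output suggests 24 h, but the nominal collection is a third of that (8/24). A summary for each time point has no evident meaning when there is one cumulative collection per period.

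**Working it through.** The plan states no window length in hours, so there is no figure of its own to reproduce. The check is arithmetic on the stated rules.

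**Step 1: window length.** Inputs: 5 h infusion (SAP 2.1), 1 h interruption (SAP 7.4), 3 h after the end (SAP 7.6.8). Formula: window W = elapsed infusion time E, including any interruption, + 3 h.

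| Course of infusion | E (h) | W (h) | W/8 |
|---|---|---|---|
| Full, uninterrupted | 5 | 8 | 100% |
| One interruption, resumed, completed | 5 + 1 = 6 | 9 | 112.5% |
| Stopped at 4 h | 4 | 7 | 87.5% |
| Stopped at 3 h | 3 | 6 | 75% |
| Stopped at 2 h | 2 | 5 | 62.5% |
| Stopped at 1 h | 1 | 4 | 50% |
| Stopped at 10 min | 0.17 | 3.17 | 39.6% |

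About 9 h is the upper limit under the hypotension algorithm, because a recurrence after resumption ends the infusion. The lower limit is just over 3 h. The longest window is thus up to about 3 times the shortest (9/3). Because resumed infusions count as completed, even the completers mix 8 h and 9 h windows.

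One case is ambiguous. If an infusion is interrupted at time s and not resumed, its end may be the last drug given (W = s + 3) or the permanent stop an hour later (W = s + 4). The SAP does not say which.

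**Step 2: effect on one patient's volume.** Let urine flow in the 3 h after the infusion be k times the flow during it. The documents give no k. Values above 1 are worth considering because oral heart failure drugs, diuretics included, are withheld until after the infusion (Protocol 7.7.1 and Table 2-2). For a stop at s hours:

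- Volume relative to a full infusion: V = (s + 3k) / (5 + 3k).
- Whole-window mL/h relative to a full infusion: R = [(s + 3k)/(s + 3)] / [(5 + 3k)/8].

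| Stop | k (assumed) | V | R |
|---|---|---|---|
| 1 h | 1 | 4/8 = 50% | 1.00 |
| 1 h | 2 | 7/11 = 64% | (7/4)/(11/8) = 1.27 |
| 1 h | 3 | 10/14 = 71% | (10/4)/(14/8) = 1.43 |
| 3 h | 1 | 6/8 = 75% | 1.00 |
| 3 h | 2 | 9/11 = 82% | (9/6)/(11/8) = 1.09 |
| 3 h | 3 | 12/14 = 86% | (12/6)/(14/8) = 1.14 |

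R exceeds 1 because post-infusion time makes up 3/8 of a full window but 3/4 of the window after a stop at 1 h.

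**Step 3: effect on a treatment mean (illustration only).** If a share x of one treatment's infusions stops early and none does on the comparator, with equal underlying flow, the mean ratio is 1 − x(1 − V).

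- x = 10%, stop at 3 h, k = 1: 1 − 0.10 × 0.25 = 0.975.
- x = 20%, stop at 1 h, k = 1: 1 − 0.20 × 0.50 = 0.90.
- x = 20%, stop at 1 h, k = 3: 1 − 0.20 × 4/14 = 0.94.

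A wider set of assumptions at k = 1 takes early stops of 5–30% on active against 0–5% on placebo, at 0.5 to 3 h, with 0 or 10% of active infusions interrupted and resumed. It gives active/placebo ratios from 0.86 to 1.00:

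- Low end: (0.30 × 3.5 + 0.70 × 8) / (0.05 × 3.5 + 0.95 × 8) = 6.65/7.775 = 0.86.
- High end: (0.05 × 6 + 0.10 × 9 + 0.85 × 8) / 8 = 8.0/8 = 1.00. Here the stops and interruptions cancel.

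Every share and stopping time in this step is assumed.

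**The case against.** **The size is uncertain, and the obvious remedy has its own bias.** A constant urine rate fits poorly with diuretics being withheld until after the infusion. Step 2 shows that the shortfall shrinks when post-infusion flow is higher and that mL/h then errs the other way. Blood-pressure stops after 4 h have windows over 7 h and, at a constant rate, lose less than 12.5%. This stands. It limits what can be said about magnitude and rules out offering the rate as a complete solution.

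**The SAP does not say that unscaled volumes will be tabulated.** It says only that output is summarised descriptively. Table details are left to a Data Presentation Plan (SAP 9) and other safety handling to the sponsor's conventions (SAP 8.1), neither of which is available. A rate defined there cannot be excluded. However, SAP 8.1 gives Section 7.6 precedence over the conventions and describes them as covering adverse events and dates. As written, 7.6.8 contains no scaling.

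**Collection times may not exist.** Neither document says that actual start and stop times of urine collection are recorded. This stands. A nominal duration can still be derived from infusion start and end, which the adverse event window already needs.

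**The impact is small.** Interruptions, reductions and discontinuations are summarised by treatment (SAP 7.4). Creatinine and BUN have marked-abnormality criteria (SAP 7.6.4), cystatin C and N-Gal are collected (Protocol 9.4.4), and urine output is not among the listed primary or secondary endpoints. The true window is stated in the sentence before the word *daily*. All of this is fair and keeps the importance low. It does not let a reader adjust the urine table, because exposure is shown separately.

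A reader might infer that the plan builds in a known bias against the active treatments. The documents do not support that: they give no stop or interruption rates by treatment, and stops and interruptions push the mean in opposite directions.

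**Conclusion.** The point holds as a low-importance improvement to a descriptive safety table. From the documents alone, the window is 8 h nominally, about 9 h after an interrupted and resumed infusion, and just over 3 h at the shortest. No scaling is stated, and *daily* describes no collection that takes place. If the table shows volumes, it can mix renal output with tolerability.

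The size cannot be settled. For a stop at 1 h the recorded volume is 50% of the full-infusion value at constant flow, or 64–71% if post-infusion flow is 2–3 times higher, which is an assumption. The effect on treatment means depends on stop rates that the documents do not give. That those rates differ by treatment is an expectation from the pharmacology described in Protocol 9.3, not a finding.

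Two stronger conclusions may tempt a reader. One is that the renal safety assessment as a whole is compromised. It is not, because it also rests on laboratory markers that do not depend on the urine collection window. The other is that converting to mL/h removes the problem at no cost. It does not, as Step 2 shows. The primary analysis of stroke volume index is unaffected.

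**What to change.** In SAP 7.6.8:

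- Drop *daily* from the title and text. Label the variable as output collected between the start of infusion and 3 h after its end.
- Replace the reference to time points with one cumulative collection per treatment period.
- Report three quantities side by side by treatment: volume (mL), collection duration (h) and mL/h.
- Take the duration from recorded urine collection times if they exist. Otherwise derive it as infusion end minus infusion start plus 3 h, and say that it is nominal.
- State which moment counts as the end of infusion when an interrupted infusion is not resumed.

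The cost is one or two derived variables and two extra rows in a table, with no change to data collection or to any other analysis. The downside is that a whole-window mL/h can overstate output after early stops, by 27–43% for a stop at 1 h if post-infusion flow is 2–3 times higher. The rate should therefore accompany volume and duration, not replace them.

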7.8 Pharmacokinetics

Blood samples will be collected from all subjects at pre-dose, 0.5, 1 and 4.5 hours during infusion and 2 hours after end of infusion and plasma concentrations will be measured using LC-MS. In addition, a PK sample will be collected from the subject when the dose is lowered due to a safety event and also at time of early discontinuation of study drug. Pharmacokinetic parameters for BMS-986231 and BMT-284730 and other metabolites (e.g., BMT-279554 and CAR-000463) will be estimated as appropriate. The plasma concentration data may also be used to conduct population pharmacokinetic analysis and exposure-response analysis with select efficacy and safety endpoints. Results of the population pharmacokinetic and exposure-response analysis will be reported in a separate report.

The PK population will be used for all listings. The Evaluable PK population will be used for summaries and statistical analyses. Geometric mean and coefficient of variation (%CV) will also

be presented for sample plasma concentration-time data. Analysis will include all analyte data in the PK dataset for BMS-986231 and metabolites of BMS-986231.

Subject plasma concentration-time profiles will be listed and summarized by treatment and nominal collection time for each analyte. Plots of mean (+SD) plasma concentration profiles versus time will be presented for each analyte, and all treatments will be superimposed on the same plot. Concentration at the end of infusion will also be summarized by treatment, which is the concentration at hour 5 for subjects completing 5 hours infusion and the concentration collected at early discontinuation for subjects not completing 5 hours infusion. The PK samples collected when the dose is lowered due to a safety event will be listed.

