Adverse Events Assessment				x		Non-serious AEs will be collected from the start of the study drug infusion, until 24 hours after end of infusion in each treatment period of dosing in each period
					x	Serious adverse events must be collected from the date of Informed consent and will be assessed up to 30 days after the end of infusion of the last period.

Table 2-2: Time & Event Schedule CV013020, Treatment and Follow-up Study Periods

Procedure	Treatment Period					Notes
	Period 1 Day 1	Washout 5-28 Days	Period 2 Day 1	Washout 5-28 Days	Period 3 Day 1	
Concomitant Medications	x		x		x	Chronic heart failure medications to be taken during the treatment day (D1 of each period) will be withheld until the end of the study drug infusion in each treatment period.
Follow-up call	x		x		x	Follow-up call to be done at Day 2 of each period (will inquire about general status and occurrence of any AEs) and 30 days after the end of the infusion of the last period (will assess occurrence of any SAEs).
Local Laboratory Tests	x		x		x	Hematology and Serum chemistry (details in the protocol section 9.4.4). Can be performed within 24 hours of treatment day.
Central Laboratory Tests	x		x		x	Hematology, Serum chemistry, Biomarkers (details in the protocol section 9.4.4)
Pharmacokinetic (PK) sampling	x		x		x	PK sampling will be done pre-dose, 0.5 hour, 1 hour, 4.5 hours and 7 hours after the start of the infusion in each treatment period. In addition, PK samples should be taken when the dose is lowered or in case of early discontinuation (see protocol section 9.5)
Pregnancy Test (WOCBP only)	x		x		x	Can be performed within 24 hours of treatment day.
Efficacy Assessments						
Echocardiography	x		x		x	Prior to and before the end of the study infusion (between hour 4 and hour 5) in each treatment period. If study drug is interrupted prematurely, the echocardiography assessment should be done as soon

Table 2-2: Time & Event Schedule CV013020, Treatment and Follow-up Study Periods

Procedure	Treatment Period					Notes
	Period 1 Day 1	Washout 5-28 Days	Period 2 Day 1	Washout 5-28 Days	Period 3 Day 1	
						Washout between periods should be at least 5 days and no more than 4 weeks.
						as possible after study drug interruption. If the study drug is resumed after interruption, echocardiography should be repeated between hour 4 and hour 5 of the effective study drug infusion.

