1	0.5 hour (± 15min)	00:30	x
1	1 hour (± 30min)	01:00	x
1	4.5 hours* (± 30min)	04:30	x
1	7 hours (± 30min)	07:00	x
1	Dose lowered due to safety event (± 30min)	Misc.	x
1	Early Discontinuation	Misc.	x

**end of the infusion sample should be taken as close to the end of the infusion as possible*

In addition, collect a PK sample from the patient when the dose is lowered due to a safety event and also at time of early discontinuation of study drug. The sample should be collected immediately before or after the decision to change the dose was made.

Blood samples will be collected from all subjects at pre-dose, 0.5, 1 and 4.5 hours during infusion and 2 hours after end of infusion and plasma concentrations will be measured using LC-MS.

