7.3 Study Population

1.1.1 Subject Disposition

Subject disposition will be listed. Summary tables reflecting the number of subjects who are enrolled, who are randomized, and reasons for not being randomized, will be presented as overall.

The number of subjects who do not complete each treatment of 5 hours infusion, both overall and according to reasons for discontinuation from the treatment, will be summarized for safety population. Subjects who have temporary interruption or down-titration of study drug but do not discontinue permanently will be analyzed as completing the treatment. The number of subjects who do not complete the study phase, both overall and according to reasons for not completing, will be summarized for safety population, as overall and by treatment group.

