8.3 Multiple Measurements

For longitudinal summaries of data, if there are multiple records within the same Hour ranges, then the value closest to the time of the planned time points is selected unless specified otherwise.

Laboratory Measurements

For tabulations of changes from baseline or shift analyses, if multiple laboratory measurements are obtained within the same nominal visit, then the measurement obtained on the day closest to the target day for that nominal visit will be used; in the case of a tie, the measurement obtained on the earlier day will be used in the analyses.

For tabulations of incidence of marked abnormalities (e.g. ALT > 3xULN), if multiple laboratory measurements are obtained within the same nominal visit, then the worst measurement within the nominal visit window nominal visit will be used.

Vital Signs and ECGs

If multiple vital sign or ECG measurements are obtained within the same nominal visit, then the measurement obtained on the day closest to the target day for that nominal visit will be used; in the case of a tie, the measurement obtained on the earlier day will be used in the analyses.

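### Does the SAP's end-of-infusion concentration need correcting because it is set at hour 5, when no PK sample is scheduled?

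*SAP*

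**What the plan says.** SAP 7.8 defines a single end-of-infusion concentration per subject and treatment. For completers it is the value "which is the concentration at hour 5 for subjects completing 5 hours infusion". For the others it is "the concentration collected at early discontinuation for subjects not completing 5 hours infusion". The same section gives the sampling scheme: "Blood samples will be collected from all subjects at pre-dose, 0.5, 1 and 4.5 hours during infusion and 2 hours after end of infusion".

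The protocol agrees with that scheme. Table 2-2 in the Schedule of Activities sets the draws at "pre-dose, 0.5 hour, 1 hour, 4.5 hours and 7 hours after the start of the infusion". Table 9.5-1 (Protocol 9.5) repeats these times with windows. It stars the 4.5 h draw, and the footnote says the "end of the infusion sample should be taken as close to the end of the infusion as possible".

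Two further provisions bear on interrupted infusions. Under Protocol 7.4, repeated in SAP 7.4, a resumed infusion runs on "to complete 5-hours of effective study drug infusion". The Subject Disposition part of SAP 7.3 adds: "Subjects who have temporary interruption or down-titration of study drug but do not discontinue permanently will be analyzed as completing the treatment".

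**The concern.** The SAP names a time that is missing from its own sampling list, and no visible text says that hour 5 means the 4.5 h draw. SAP 7.8 summarises concentration profiles by nominal collection time. A programmer who selected nominal hour 5 would therefore find no completers, and the table would hold only early-discontinuation values.

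The obvious repair, reading hour 5 as the 4.5 h draw, looks weaker for subjects whose infusion was paused and resumed. If the draw stays on clock time, their value comes from mid-infusion or from the pause itself, yet it would be pooled with true end-of-infusion values. At stake are the content of one PK summary and the chance that samples are chosen after the data are seen.

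**Working it through.** The SAP gives no figure to reproduce, so the check sets the sampling times beside the infusion times.

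**Inputs.** Draw times and windows come from Protocol Table 9.5-1: 0.5 h ±15 min, 1 h ±30 min, 4.5 h ±30 min and 7 h ±30 min, plus a pre-dose draw. Infusion length is 5 h. An interruption lasts 1 h and applies to events in the first 4 h (Protocol 7.4). Protocol 8.1 requires discontinuation if hypotension recurs after resumption, so one pause per infusion is the case to examine. I assume prompt resumption.

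**Step 1: does any draw match hour 5?** The windows are 0.25–0.75, 0.5–1.5, 4.0–5.0 and 6.5–7.5 h. No nominal time equals 5, so 0 of 5 scheduled draws per period match. Only the 4.5 h window reaches 5.0 h, at its upper edge.

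**Step 2: uninterrupted infusion.** This includes infusions that were only down-titrated, which still end on schedule.
- End of infusion: 5.0 h.
- Designated draw: 5.0 − (4.0 to 5.0) = 0 to 1.0 h before the end.
- Post-infusion draw: 5 + 2 = 7 h, so the SAP's description and the protocol's clock time agree.
- The draw before the designated one is at 1 h and the draw after it is at 7 h. Only the 4.5 h draw can be the end-of-infusion sample.

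**Step 3: one pause, then resumed, with draws on clock time.**
- End of infusion: 5 + 1 = 6.0 h.
- Designated draw: 6.0 − (4.0 to 5.0) = 1.0 to 2.0 h before the end; at nominal 4.5 h, 6.0 − 4.5 = 1.5 h before.
- A pause starting at time s covers s to s + 1. It contains 4.5 h when s lies between 3.5 and 4.0 h.
- Drug time delivered by clock hour 5: 5 − 1 = 4 h.

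**Step 4: the same subject, with draws on infusion time.**
- 4.5 h of infusion falls at clock 4.5 + 1 = 5.5 h if the pause came earlier, with a window of 5.0–6.0 h.
- Designated draw: 6.0 − (5.0 to 6.0) = 0 to 1.0 h before the end, the same as in an uninterrupted infusion.

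**Step 5: which reading do the documents support?** Table 2-2 counts from the start of the infusion and Table 9.5-1 counts relative to dose, which favours clock time. The SAP's description of draws during infusion, the footnote asking for a sample near the end, and the use of effective infusion time in Protocol 7.4 and SAP 7.4 favour infusion time. Both 7.4 sections also call for end-of-infusion procedures promptly after an interruption, without saying whether PK is one of them. The text does not decide between the readings.

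**Step 6: would a stricter rule help?** Suppose the summary accepted only samples within 1 h of the actual end, matching the 4.0–5.0 h window. On clock time (step 3), only a draw at exactly 5.0 h would qualify. Nearly all resumed subjects would drop out while early discontinuers stayed in. On infusion time (step 4), all in-window draws qualify and the rule does nothing.

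**The case for a change.** The strongest case for a change is that the inference in step 2 does not cover everyone the SAP may count as a completer. After a resumed infusion, Protocol Table 2-2 and section 9.1.1 re-time the echocardiogram to effective infusion hours, but nothing equivalent is said for PK. Sites may therefore differ. On clock time, hour 5, the 4.5 h draw and the true end are three different times. A wording fix needs about two SAP sentences and no new samples, so leaving the choice to the analyst gains nothing.

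Some of this stands. The SAP wording is wrong as written, and PK timing after resumption is unsettled.

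Other parts carry less weight:
- The disposition rule on interrupted subjects sits in SAP 7.3, and SAP 7.8 does not say that it governs PK.
- SAP 8.3, under which "the value closest to the time of the planned time points is selected unless specified otherwise", chooses among several records in the same hour range. It was never meant to map hour 5 to a draw, so its silence proves little.
- An empty completer row requires someone to overlook the protocol footnote and accept a table that is visibly wrong.
- The empty row and the mixed values come from different implementations and cannot both occur.
- The summary is mixed by design. It includes early-discontinuation values, and resumed subjects finish at half the dose, so exact timing would not make their values comparable with the rest.
- SAP 8.4 lists all concentration data and refers PK analysis and reporting to a separate sponsor document. SAP 9 leaves table details to a Data Presentation Plan. Neither was available, and either may contain the mapping.

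**Conclusion.** No change to the plan is needed. For uninterrupted infusions this is a clerical mismatch: the intended sample is the 4.5 h draw, taken 0 to 1.0 h before the end, and the protocol identifies it. For resumed infusions the documents leave a true ambiguity. On clock time the draw precedes the end by 1.0 to 2.0 h; on infusion time, by 0 to 1.0 h. The 1 h cutoff examined above would either remove almost all of these subjects or have no effect, so it is a debatable trade-off.

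The consequence is confined to one descriptive PK summary. The primary and secondary efficacy models do not use the value, and no conclusion about stroke volume index depends on it. The conclusion assumes that analysts read the Table 9.5-1 footnote and that resumption is prompt after a single 1 h pause. Two things are unknown: the documents give no expected number of interrupted subjects, and the SAP was written against Revised Protocol 02, whereas Table 9.5-1 is read here from Revised Protocol 05. The second matters little, because the SAP's own list already has the 4.5 h draw and no 5 h draw.
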